#### 4.3. Subgroup Analysis of Primary Efficacy Endpoint

The subgroup analysis in this chapter will adopt the primary event censoring rules. Subgroup analysis is expressed as follows:

- 1) Based on the full analysis set, the following analysis is performed on the subgroup level in the two subgroups of EGFR gene mutation type and brain metastasis status based on PFS as evaluated by the investigator:  
Kaplan-Meier plots are drawn for the two treatment groups and the median and 95% confidence interval of PFS in the two treatment groups are given.
- 2) The above analysis is repeated based on PFS as evaluated by the IRC.
- 3) In addition, based on the full analysis set, the Cox proportional hazards model is adopted for subgroup analysis of the subgroups defined in [Section 2.2.3](#) based on PFS as evaluated by the investigator. The HR and 95% confidence interval of the PFS comparison between the two treatment groups on the subgroup level are given.  
The HR and corresponding 95% confidence interval calculated in different subgroups will be displayed as a forest plot and the above analysis results will be displayed in the plot.  
Note: For subgroups with too few events (that is, the number of events on the subgroup level is lower than 20), the analysis results for the subgroup will not appear in the forest plot.

#### 4.4. Secondary Efficacy Endpoint Analysis

##### 4.4.1. Objective response rate (ORR)

The following analysis of the endpoint will be performed based on the FAS:

- 1) The number and percentage of best tumor response results based on treatment group are summarized as follows: Complete response (CR), partial response (PR), stable disease (SD), progressive disease (PD), and not evaluable (NE).
- 2) The number of cases that achieved an objective response and the objective response rate (as a percentage) as well as the 95% Clopper-Pearson confidence interval for the response rate in each treatment group are calculated and summarized. In ORR analysis, evaluations performed after subject progression are not included in the analysis. If a subject uses other non-investigational drugs for anti-tumor therapy after terminating the investigational drug treatment, any CR or PR occurring from the time of use will not be included in the numerator of the ORR calculation.
- 3) A logistic regression model stratified by EGFR mutation type and brain metastasis status is used for the Wald Chi-squared test to compare the objective response rates of the two treatment groups. The odds ratio (OR) estimate and 95% confidence interval calculated based on the Wald method are given.

##### 4.4.2. Duration of response (DoR)

The following analysis of the endpoint is performed on all subjects with an objective response based on the FAS:

The same method as the primary endpoint PFS is adopted for analysis. The Kaplan-Meier estimates of progression-free response rate at 6, 9, 12, 15, and 18 months as well as the 95% confidence intervals corresponding to the K-M estimates based on Greenwood's standard error estimation method are given.

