12.3.2.2 Analysis of Secondary Efficacy Endpoints

- **Analysis of Overall Survival**

The analysis method and model for calculating overall survival are the same as those used for PFS, provided that the requirements for the number of events for the analysis is met. In addition, the proportion of events occurring within 12, 24 and 36 months will be summarized.

- **Analysis of Objective Response Rate**

For the analysis of objective response rate, the odds ratio (OR), its 95% CI and p-value will be calculated using logistic regression analysis with the same stratification factors presented above.

ORR values will be summarized by treatment group and stratification factors, respectively.

- **Analysis of Duration of Response**

The analysis of duration of response will be the same as the primary analysis with the same stratification factors as above. Kaplan-Meier plots will be plotted to calculate the median and 95% CI of DoR in each group and p-value.

- **Analysis of Disease Control Rate**

For the analysis of disease control rate, the OR value and its 95% CI and p-value will be calculated using logistic regression analysis with the same stratification factors as above.

- **Analysis of Depth of Response**

Descriptive statistics will be used to summarize the change from baseline and percentage change of the sum of diameters of target lesions at different visit points. The depth of response (taking the maximum change of the sum of diameters of target lesions) will be compared between the two groups using analysis of covariance, and the unrounded mean, least squares mean, difference between the two groups, and 95% CI of the difference in each group, and p-value will be calculated.

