The log-rank test stratified by EGFR mutation type and brain metastasis status will be used to compare the PFS distributions of the HS-10296 group and the gefitinib group to determine whether there are statistical differences. This test is a two-tailed test with a level of significance of 0.05. The results will be given as test p values.

Kaplan-Meier plots of the two treatment groups are drawn and the 1/4 quantile, median value, and 3/4 quantile of the PFS of the two treatment groups as well as the 95% confidence intervals for each quantile are given. The Kaplan-Meier estimates of progression-free survival at 6, 12, 18, and 24 months as well as the 95% confidence intervals corresponding to the K-M estimates based on Greenwood's standard error estimation method are given.

The stratified Cox proportional hazards model is used to estimate the PFS hazard ratio (HR) of the two treatment groups and the 95% confidence intervals corresponding to the estimates are given. The reasonableness of the proportional hazards assumption in this model will be tested.

The above two tests use subjects' actual stratification information during the screening period for analysis.

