14.2.13 Analysis of objective response and disease control-full analysis set
Table 14.2.13.1 Statistical analysis of objective response rate and disease control rate as evaluated by investigator-full analysis set
Table 14.2.13.2 Statistical analysis of duration of response as evaluated by investigator-full analysis set (only including subjects with objective response)
Figure 14.2.13.1 Kaplan-Meier curve based on PFS as evaluated by the investigator-full analysis set

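### Duration of response is tested between arms in responders only, so its p-value and HR are biased if the responders gained on one arm have different durations

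*SAP*

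**What the plan says.** SAP 4.4.2 restricts the DoR analysis to responders: "The following analysis of the endpoint is performed on all subjects with an objective response based on the FAS". It continues: "The same method as the primary endpoint PFS is adopted for analysis". SAP 4.1 says what that method is. The test is two-tailed at 0.05: "The log-rank test stratified by EGFR mutation type and brain metastasis status will be used to compare the PFS distributions". The estimate comes from a Cox model: "The stratified Cox proportional hazards model is used to estimate the PFS hazard ratio (HR) of the two treatment groups".

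Protocol 12.3.2.2 agrees: "The analysis of duration of response will be the same as the primary analysis with the same stratification factors as above". It asks for Kaplan-Meier plots "to calculate the median and 95% CI of DoR in each group and p-value". In the SAP list of tables, Table 14.2.13.2 carries the same restriction: "full analysis set (only including subjects with objective response".

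DoR is one of the measures that the secondary objective sets out to compare between arms (protocol 5.1.2, SAP 1.1.2). Its clock starts at first response (protocol 12.1.5, SAP 1.3.2). Neither document calls the DoR comparison descriptive or adds a caveat, and neither plans a time-in-response analysis in all FAS patients.

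**The concern.** Response is an outcome of treatment, so both membership of the DoR population and its time zero are fixed after randomization. The HS-10296 responders and the gefitinib responders are therefore not randomized groups. Suppose one drug also turns harder-to-treat patients into responders, and their responses are short. They then pull down that arm's DoR curve even if the drug shortens nobody's response. If the gained responders last longer than the rest, the error runs the other way.

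The documents give some reason to expect a different mix of responders:

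- Protocol 4.1 puts primary T790M at about 30% of EGFRm+ patients with sensitive assays. By its title, the study cited for this links pretreatment T790M to shorter response on EGFR TKIs. Protocol 4.2 says HS-10296 inhibits T790M.
- SAP 4.2 plans a sensitivity analysis for primary resistance.
- SAP 1.3.2 does not require confirmation of CR or PR, so marginal responses enter the DoR population.
- SAP 4.4.1 tests ORR between arms, so the plan allows that treatment changes who responds.

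At stake is an HR and p-value that would be read as a randomized efficacy comparison.

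**Working it through.** **1. The plan's own figures.** The documents state no ORR, DoR or power for the DoR comparison. The figures in protocol 5.3 are for PFS, and they reproduce. Schoenfeld events = 4(1.960 + 1.282)²/(ln 0.67)² = 42.03/0.1604 = 262.1, and 262 events give 90.0% power. Nothing below changes them.

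**2. A check by hand.** Let a share *q* of test-arm responders be patients who would not have responded on control. Let the drug have no effect on duration in patients who would respond on either arm (assumed median 10 months), and let the extra responders have median *m*, all exponential. At the start of follow-up the apparent HR is

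(1 − q) + q × (10/m).

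For ORR 70% vs 80%, q = 10/80 = 0.125. With m = 5, the HR is 0.875 + 0.125 × 2 = 1.125. It then drifts toward 1 as the short responders leave the risk set. With m = 10 it is exactly 1.

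**3. Simulation of the same model.** There were 205 patients per arm (410/2), entry uniform over 8 months, cutoff at 23 months (protocol 5.3), response assumed at 1.4 months, an unstratified log-rank test in responders, and 4,000 trials per row. ORR and durations are assumed.

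| ORR control/test | m (months) | q | HR at start | Apparent HR | Rejection |
|---|---|---|---|---|---|
| 70/70 | none | 0 | 1.00 | 1.00 | 4.9% |
| 70/85 | 10 | 0.176 | 1.00 | 1.00 | 4.8% |
| 70/80 | 5 | 0.125 | 1.125 | 1.08 | 9.4% |
| 70/85 | 5 | 0.176 | 1.18 | 1.12 | 13.2% |
| 60/80 | 5 | 0.25 | 1.25 | 1.17 | 20.1% |
| 70/85 | 3 | 0.176 | 1.41 | 1.19 | 26.1% |
| 70/85 | 20 | 0.176 | 0.91 | 0.89 | 12.8% |

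Where the extra responders are short-lived, nearly all rejections go against HS-10296. With m = 20 they go in its favour.

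**4. Masking.** Now let the drug truly lengthen response (HR 0.667) in patients who would respond on either arm, with m = 5. Rejection is 76.8% at 70/70. It falls to 44.6% at 70/80 (apparent HR 0.76), 32.6% at 70/85 (0.81) and 15.6% at 60/80 (0.87).

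**5. A second model.** Here each patient has a normal latent sensitivity *u*. A patient responds if *u* passes the cut for the stated ORR. Duration is exponential with log-mean rising by 0.5 or 1.0 per unit of *u*, there is no drug effect on duration, and censoring is uniform from 13 to 21 months. Three sets of runs (400, 2,000 and 4,000 trials per scenario, with different assumed baseline durations) gave these combined ranges:

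| ORR | Apparent HR | Rejection |
|---|---|---|
| equal | 1.00 | 5 to 6% |
| 70/75 (4,000-trial set only) | 1.04 to 1.07 | 5.4 to 6.9% |
| 70/80 | 1.07 to 1.15 | 5 to 14% |
| 65/80 | 1.11 to 1.24 | 11 to 26% |

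The 5% lower end at 70/80 comes from the 400-trial set, where the standard error is about 1 to 2 points. The two larger sets start at 7.5 to 8%.

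**The case against.** DoR is one of five secondary efficacy endpoints. Sample size, power and alpha are set for PFS, and no success claim hangs on DoR. The table title discloses the restriction to responders. ORR is compared in the FAS by randomized arm, so a reader can see an imbalance in response. Every magnitude above depends on chosen ORR gaps and durations, and at a 5-point gap the effect nearly vanishes. With shorter-lasting extra responders the error penalizes the sponsor's own drug: in the 4,000-trial set of the second model, false findings of longer DoR on HS-10296 fell to 0.1 to 0.7% at 70/80 and 0.0 to 0.4% at 65/80, against a nominal 2.5%. A bias toward HS-10296 appeared only when the extra responders were assumed to last twice as long as the rest. Finally, restricted mean time in response is a different quantity from DoR.

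Most of this stands, and it limits the point to the interpretation of a secondary endpoint. Two parts do not remove it. Disclosing the population does not give the p-value a randomized meaning. Seeing an ORR difference does not tell a reader how far it has moved the DoR HR.

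**Conclusion.** The point holds, with a condition. The planned DoR test and HR compare groups formed after randomization. They are biased as measures of drug effect on duration when the arms differ in who responds and the responders gained on one arm differ in duration from the others. The direction is not fixed. On the assumed inputs, the apparent HR under no drug effect on duration is about 1.07 to 1.15 at ORR 70/80 and 1.11 to 1.24 at 65/80. These sizes are illustrations, not predictions for this trial. The simulated tests in the first model are unstratified. Stratifying by mutation type and brain metastasis would remove only the part of the imbalance that those two factors explain.

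A reader might infer that a higher response rate by itself distorts DoR. It does not: at 70/85 with equal durations the HR was 1.00 and rejection 4.8%. A reader might also infer that the plan tilts the result toward HS-10296. The documents give no ORR or DoR assumption that would support this, and the simulations with shorter-lasting extra responders point the other way. The primary PFS comparison, the 262 events and the 410 patients are untouched.

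**What to change.** In SAP 4.4.2, keep the per-arm Kaplan-Meier curves, the quartiles and the 6- to 18-month rates with confidence intervals. All of these are already planned. Drop the DoR p-value and HR, or label them descriptive and non-randomized. Carry the change into Table 14.2.13.2, and record it in SAP section 6 as a departure from protocol 12.3.2.2.

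If a between-arm comparison is wanted, add restricted mean time in response over all FAS patients by randomized arm. One way is the area between two Kaplan-Meier curves in each arm: PFS, and time to the earlier of first response or PFS event. This gives non-responders no time in response and handles patients censored before any response. The SAP should state three things:

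- the truncation time, fixed before unblinding (planned minimum follow-up is 23 − 8 = 15 months, which is one anchor);
- the censoring rule, for example Table 4.1-2 for both curves;
- that the measure combines how often patients respond with how long responses last.

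The cost is an inferential DoR p-value given up, some SAP wording and one more table. The data are already collected.

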#### 4.4.3. Disease Control Rate (DCR)

The following analysis of DCR based on the FAS will be performed:

- 1) Descriptive summarization of DCR by treatment group is performed. The DCR estimate and 95% Clopper-Pearson confidence interval of each treatment group is estimated.
- 2) A logistic regression model stratified by EGFR mutation and brain metastasis status is adopted to compare the DCR of the two treatment groups. The estimated odds ratio (OR), 95% confidence interval, and test p value of DCR of the two treatment groups are given.

#### 4.4.4. Depth of response (DepOR)

The following analysis of this indicator is performed based on the FAS.

- 1) Based on visit, the number of subjects included in the calculation and absolute change and relative percentage change in tumor size versus baseline in the two treatment groups are descriptively summarized. At the same time, the means, standard deviations, 1/4 quantiles, medians, 3/4 quantiles, minimums, and maximums are also given.
- 2) The best percentage of tumor response by treatment group is summarized. The number of subjects included in the calculation and the mean, standard deviation, minimum, maximum, and median of the best percentage in each treatment group are given; and the numbers and proportions of subjects who achieved a 30%, 50%, and 75% tumor response are calculated.
- 3) The ANCOVA model is adopted for comparison of best percentage of tumor response between groups. The covariates in the model include EGFR mutation type, brain metastasis status, the sum of the diameters of all evaluable target lesions at baseline (mm), and the time interval from the baseline scan date to the date of randomization (days). The analysis results provide the number of subjects included in the calculation, the corrected mean best percentage, and the corresponding 95% confidence interval of each treatment group. At the same time, the estimated least squares mean of the comparison between the two groups, the 95% confidence interval, and the test p value are given (level of significance of 0.05).
- 4) Waterfall plots of best percentage of tumor response by treatment group are drawn. In the plots, two reference lines of the best percentage are marked: 20% (indicating a 20% increase in tumor size versus baseline, corresponding to disease progression as defined by RECIST V1.1) and -30% (indicating a 30% decrease in tumor size versus baseline, corresponding to partial response as defined by RECIST V1.1).

#### 4.4.5. Overall survival (OS)

Overall survival OS is performed separately in the FAS and PPS.

If the subject's date of survival or death is confirmed to be later than the data cutoff date, the survival period of the subject is censored to the data cutoff date. If it is not known whether the subject has died, it will be censored to the latest known date of survival recorded in the EDC.

- 1) The same method as the primary endpoint PFS is adopted for analysis. The Kaplan-Meier estimates of overall survival rate at 12, 24, and 36 months and corresponding 95% confidence intervals are given.
- 2) If the data are mature, the same subgroup analysis method as PFS will be adopted for analysis of OS.

## 5. Safety Analysis

All safety analysis will be based on the safety set.

### 5.1. Adverse events

Adverse events will be coded with MedDRA 23.0 or a higher version.

CTCAE (4.03) will be obtained for the rating of the seriousness of adverse events. AEs that occur from the start of treatment to within 28 days after the last treatment will be summarized in the safety evaluation. AEs occurring prior to treatment initiation and AEs occurring within 28 days after the last treatment are tabulated separately and will not be included in summary tables for AEs.

General principles to follow when summarizing adverse events:

- 1) Adverse events are summarized by treatment group and system organ class/preferred time (SOC/PT).
- 2) If the same subject has the same adverse event multiple times, the one with the highest correlation with the investigational drug will be used to summarize the investigational drug-related AE and the one with the highest severity will be used for the summary of adverse event seriousness.
- 3) Only adverse events during the randomized, double-blind treatment stage and not during the cross-treatment stage are included.

All of the AEs of each subject will be presented in a list.

Related to the investigational drug refers to “definitely related,” “possibly related,” and “unable to be determined.”

Serious adverse events will be summarized and tabulated individually.

The following summary results will be given:

- 1) Summary of all adverse events
- 2) All adverse events summarized by system organ class and preferred term
- 3) Investigational drug-related adverse events summarized by system organ class and preferred term
- 4) All common adverse events summarized by system organ class and preferred term
- 5) All common investigational drug-related adverse events summarized by system organ class and preferred term
- 6) Adverse events of CTCAE grade  $\geq 3$  summarized by system organ class and preferred term
- 7) Investigational drug-related adverse events of CTCAE grade  $\geq 3$  summarized by system organ class and preferred term
- 8) Serious adverse events (SAEs) summarized by system organ class and preferred term
- 9) Investigational drug-related serious adverse events (SAEs) summarized by system organ class and preferred term
- 10) Adverse events leading to permanent discontinuation summarized by system organ class and preferred term
- 11) Investigational drug-related adverse events leading to permanent discontinuation summarized by system organ class and preferred term

- 12) Adverse events leading to suspension of medication summarized by system organ class and preferred term
- 13) Investigational drug-related adverse events leading to suspension of medication summarized by system organ class and preferred term
- 14) Adverse events leading to dose reduction summarized by system organ class and preferred term
- 15) Investigational drug-related adverse events leading to dose reduction summarized by system organ class and preferred term
- 16) All adverse events leading to death summarized by system organ class and preferred term
- 17) All adverse events and serious adverse events are given in the list of all investigational drug-related adverse events leading to death summarized by system organ class and preferred term.

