12.2 Safety Evaluation

At the end of the study, all safety data will be summarized. All data from the start of treatment until 28 days after the last treatment will be summarized in the safety assessment. Data obtained prior to the initiation of treatment will be summarized but not included in the summary table of AEs.

The number of subjects with each AE will be summarized by Medical Dictionary for Regulatory Activities (MedDRA) system organ class (SOC), MedDRA preferred term (PT) and CTCAE grade. The number and percentage of subjects with AEs of different categories (e.g., the relationship to the investigational product, or CTCAE Grade 3 or higher) will be summarized by group. In addition, adverse events of each category will also be further summarized by MedDRA system organ class and preferred term by group. Serious adverse events will be separately summarized. The events of death will be tabulated in detail by subject.

Any AE that occurs prior to the subject's first dose (i.e., prior to Study Day 1) will be tabulated but will not be included in the summary tables of AEs. Any AE occurring during the specified 28-day follow-up period after a subject discontinues the study treatment will be included in the AE summary report; any AE that occurs after the subject discontinues the treatment with the investigational product and has received other further anti-tumor therapy during that follow-up period will be flagged in the data tables. Adverse events that occur during the 28-day follow-up period after the discontinuation of the investigational product will be tabulated separately and will not be included in the AE summary report. For subjects that can continue to derive benefit in the opinion of the Investigator after disease progression and continue to receive study treatment, the AEs occurred in these subjects will be tabulated separately and will not be included in the summary tables of AEs.

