12.3.3 Safety Analysis

12.3.3.1 Adverse Event

AEs occurring from treatment initiation until 28 days after the last dose will be summarized in the safety evaluation. AEs that occur prior to the initiation of study treatment and those occurring 28 days after the last dose will not be included in the summary table of AEs.

Adverse events occurring post-dose will be summarized by treatment group, mainly including:

- 1) The number and proportion of patients with at least one AE;
- 2) The number and proportion of patients with at least one study drug-related AE;
- 3) The number and proportion of patients with at least one AE of higher severity (CTCAE Grade ≥ 3);
- 4) The number and proportion of patients with at least one study drug-related AE of higher severity (CTCAE Grade ≥ 3);
- 5) The number and proportion of patients with at least one SAE;
- 6) The number and proportion of patients with dose modifications due to AEs;
- 7) The number and proportion of patients who have withdrawn from the study due to AEs;
- 8) The number and proportion of patients who died due to AEs.

Adverse events will be summarized by system organ classes and preferred terms. All adverse events will be tabulated.

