16.2.7 Lists of adverse events	List 16.2.7.1 List of all adverse events (during treatment and 28 days after the last medication)-safety set List 16.2.7.2 List of all adverse events (before the first medication)-safety set List 16.2.7.3 List of all adverse events (28 days after the last medication)-safety set List 16.2.7.4 List of all serious adverse events-safety set

List 16.2.7.5 List of adverse events leading to death-safety set
16.2.8 Laboratory tests, ECGs, LVEF, ECOG PS scores, etc.
List 16.2.8.1 List of laboratory test results (routine blood)-safety set
List 16.2.8.2 List of laboratory test results (blood chemistry)-safety set
List 16.2.8.3 List of laboratory tests (routine urine)-safety set
List 16.2.8.4 List of examination results of vital signs (including weight and ECOG PS score)-safety set
List 16.2.8.5 List of physical examination results-safety set
List 16.2.8.6 List of 12-lead ECG examination results-safety set
List 16.2.8.7 List of LVEF test results-safety set
List 16.2.8.8 List of ophthalmological examination results-safety set

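### SAP 5.1 and protocol 12.2 each place adverse events from the 28 days after last treatment both inside and outside the AE summaries

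*SAP*

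**What the plan says.** **SAP 5.1.** One sentence includes the post-treatment window: "AEs that occur from the start of treatment to within 28 days after the last treatment will be summarized in the safety evaluation". The next deals with AEs before treatment and with the post-treatment window together, and for the latter says "AEs occurring within 28 days after the last treatment are tabulated separately and will not be included in summary tables for AEs".

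**Protocol 12.2.** The section opens by including the window: "All data from the start of treatment until 28 days after the last treatment will be summarized in the safety assessment". Later it says that an AE in the specified "28-day follow-up period after a subject discontinues the study treatment will be included in the AE summary report", and that such events will be flagged if the subject has meanwhile received other anti-tumor therapy. The following sentence begins "Adverse events that occur during the 28-day follow-up period after the discontinuation of the investigational product will be tabulated separately" and goes on to leave those events out of that same report.

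**Protocol 12.3.3.1.** The first sentence reads "AEs occurring from treatment initiation until 28 days after the last dose will be summarized in the safety evaluation". The second sets aside AEs before treatment and "those occurring 28 days after the last dose will not be included in the summary table of AEs", this time with no word such as within or during.

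**SAP listings (section 7, 16.2.7).** List 16.2.7.1 is titled "List of all adverse events (during treatment and 28 days after the last medication)-safety set". List 16.2.7.2 covers AEs before first medication. The title of List 16.2.7.3 mentions 28 days after last medication but does not say whether it means up to or beyond that day.

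**The concern.** Comparing the safety of the two drugs is a stated secondary objective. Protocol 9.1.3.2 sets up a contact at 28 days partly to pick up new AEs, and protocol 11.1.3.1 runs AE collection to the end of that period. A rule that keeps those events out of the summary tables would collect them and then not count them.

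The two sentences in SAP 5.1 cannot both be obeyed, and no other SAP passage says which governs. A programmer who followed the explicit exclusion would be following the SAP. AEs, SAEs and fatal AEs starting after the last dose would then be missing from the between-arm counts in the tables that readers use first: the overall AE summary (14.3.1.1), SAEs (14.3.1.6) and AEs causing death (14.3.1.16).

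**Working it through.** There is no planned figure to reproduce, so the check compares the texts.

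**1. Do the sentences cover the same window?**

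| Place | Instruction for AEs starting up to 28 days after last dose |
|---|---|
| SAP 5.1, including sentence | In |
| SAP 5.1, next sentence | Out |
| Protocol 12.2, opening | In |
| Protocol 12.2, follow-up sentence | In |
| Protocol 12.2, next sentence | Out |
| Protocol 12.3.3.1, first sentence | In |
| Protocol 12.3.3.1, second sentence | Unclear: can be read as beyond day 28 |

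In SAP 5.1 the included interval runs from first dose to last dose + 28 days. The excluded set is everything before first dose, plus last dose to last dose + 28 days. The two overlap on the whole post-treatment window. The pair in protocol 12.2 overlaps in the same way.

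**2. Can the pair be read as two different outputs?** One could take the including sentence to mean a separate summary and the excluding one to mean the main tables. Protocol 12.2 rules this out for itself, because it names the same summary report in both sentences. In the SAP, the planned AE tables (14.3.1.1 to 14.3.1.27) include none reserved for the 28-day window; only listings are split by period.

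**3. Does another passage settle it?**
- The opening of protocol 12.2, the first sentence of 12.3.3.1, the title of List 16.2.7.1 and the purpose of the 28-day follow-up all point towards inclusion.
- SAP 2.2.8.3 decides whether an AE occurred during treatment only by comparing its start with the date of first medication. It sets no upper limit.
- Principle 3 of SAP 5.1 restricts the tables to the randomized double-blind treatment stage and excludes the crossover stage. It does not say whether post-treatment follow-up belongs to the former.

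The evidence leans one way but does not resolve the conflict.

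**4. What would the excluding sentence do to a count?** For a table of subjects with at least one qualifying AE:

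count under exclusion = count under inclusion − number of subjects whose qualifying AEs all start in the 28 days after last dose.

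A subject with another qualifying AE on treatment stays in. In tables by severity, which take the highest grade, such a subject could still move to a lower grade. The subtracted term needs AE rates in the window and rates of stopping treatment. The documents give neither, so it cannot be computed for either arm.

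**5. Where must the window be cut?** Protocol 6.1 requires a gefitinib washout of at least 10 days before crossover. With the earliest permitted start, up to 28 − 10 = 18 days of the window could overlap open-label HS-10296. Protocol 9.2.2.1 also records AEs in a pre-crossover period of up to 28 days that begins at crossover consent. The SAP does not say at which point the crossover stage starts.

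**The case against.** The strongest reply is that this is an evident slip. Because both sentences cannot be programmed, someone would have to ask. The events stay in the listings (16.2.7.1, 16.2.7.4 and 16.2.7.5), the AE tables are descriptive, and no test depends on them. All of that stands and limits the seriousness. It does not remove the contradiction, which sits in both documents.

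Some stronger readings are tempting, but the documents do not support them:

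- *SAP Section 6 records only the change to overall survival, so the exclusion cannot be a deliberate departure.* Section 6 is not a full record. SAP Table 4.1-2 censors PFS at termination of treatment, while protocol 12.1.3 follows patients to progression. SAP 1.3.2 adds a 35-day minimum for stable disease that protocol 12.1.6 lacks. Neither is recorded there, so its silence shows nothing about intent.
- *The second sentence of protocol 12.3.3.1 can only mean beyond day 28.* That is the more natural reading after its first sentence, but the wording does not force it.
- *The three listings must be mutually exclusive, so 16.2.7.3 must be beyond day 28.* Lists 16.2.7.4 and 16.2.7.5 already overlap 16.2.7.1, and a separate listing of the 28-day events would also fit the literal text of SAP 5.1.
- *One mistaken word, within for more than, explains everything.* It could explain SAP 5.1. It does not explain protocol 12.2, which places the excluded events during the 28-day follow-up period.
- *The number of tables measures the damage.* The rule reaches all 27 AE tables, but several recombine others, and those on suspension, dose reduction or discontinuation would seldom gain an AE that starts after the last dose. The count shows reach and is not an effect size.

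**Conclusion.** Wrong as written. SAP 5.1 and protocol 12.2 each include and then exclude the same AEs, and nothing else in the documents decides between the two instructions. The likely intent is to exclude AEs starting later than 28 days after last dose, but this is an inference from the surrounding text.

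The consequence is conditional: it arises only if the excluding sentence is the one programmed. The comparative AE, SAE and fatal-AE tables would then omit events starting in the 28 days after last dose, and those events would appear only in listings. Neither the size nor the direction between arms can be calculated. A reader might infer that the exclusion favors one drug; the documents give no rates that would support this. The primary endpoint and all planned tests are unaffected. The point merits correction before database lock because safety comparison is a stated objective and the correction is nearly free.

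**What to change.** Before database lock:

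1. Reword SAP 5.1 so that the AE summary tables include AEs starting from first dose to 28 days after last dose, and only AEs before first dose or more than 28 days after last dose are listed separately.
2. Give the on-treatment definition in SAP 2.2.8.3 the same upper limit.
3. Retitle List 16.2.7.3 so that it says more than 28 days after last medication.
4. Record the change in the SAP revision history.
5. Align protocol 12.2 at its next amendment.

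Two boundaries are for the sponsor to define:

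- **Crossover.** State whether the window ends at pre-crossover consent or at the first crossover dose, consistently with principle 3 of SAP 5.1, and whether the randomized stage in that principle includes post-treatment follow-up.
- **Treatment beyond progression.** Protocol 12.2 keeps AEs of these subjects out of the summary tables, and SAP 5.1 is silent. Protocol 10.2.3 describes the drug given after progression as the original study treatment, so a window tied simply to last dose would bring those AEs back in. The two documents must be reconciled, including whether the protocol sentence covers only AEs that start after progression.

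The cost is a few wording changes, one listing title and a revision-history entry, with no new data and no added analyses. The protocol amendment may need notification to the IRB or IEC under protocol 15.1.
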